### **Funding**

Deutsche Stiftung Neurologie (DSN)

## Summary

The study is designed to assess the effects of cardiovascular (aerobic) exercise on motor skill learning in Parkinson patients. Specifically, we examine whether learning a novel motor skill over a six-week period is enhanced when skill practice sessions are combined with additional moderate-intense aerobic exercise bouts. In this randomized controlled trial, participants will be allocated to either an intervention group (motor skill practice + aerobic exercise) or control group (motor skill practice + seated rest).

## Background

Parkinson's disease (PD) is a progressive neurodegenerative disorder that is characterized by motor control impairments, such as gait disturbances and postural instability. Beneficial effects of exercise are attributed to mechanisms of neuroplasticity, and task-specific motor training (repeated practice of a skill) is consequently considered to be a motor learning process. Importantly, the formation (acquisition) and consolidation of motor memories is impaired in PD compared to healthy individuals of similar age.

Thus, it is crucial to identify strategies to enhance motor learning in people with PD. Recent studies have accumulated evidence to show that acute (single bouts of) and chronic (multiple bouts of)

---

cardiovascular exercise can facilitate motor skill learning. However, this evidence is mainly derived from studying healthy individuals. In a first study including PD patients, we recently found improved motor memory consolidation, but not skill acquisition, when practice was preceded by a single bout of cardiovascular exercise.

These results suggest that acute exercise may enhance motor memory formation processes, but could potentially interfere with motor skill acquisition when performed prior to practice. Consequently, in a second study including PD patients, we changed the design so that a bout of cardiovascular exercise immediately followed skill practice, and found that exercise facilitated motor memory consolidation as indicated by improved offline learning gains.

Going onward from the previous two studies, the present study will investigate the effects of performing cardiovascular exercise immediately following skill practice over a six-week intervention period on motor memory consolidation. It will be examined how the regular direct coupling of motor learning skill practice and cardiovascular exercise influences the consolidation and automation of the practiced movements.

## Aims/Hypothesis

The main question of the study is whether moderate-intense aerobic exercise, performed immediately following motor skill practice over a six-week intervention period, facilitates motor memory consolidation in Parkinson's Disease (PD).

### Hypotheses:

1. Learning a novel balance task over a period of six weeks is enhanced when cardiovascular exercise bouts are performed immediately following each skill practice session.
2. We further hypothesize, that improved learning outcome with exercise will result from improved motor memory consolidation (offline gains between practice sessions).

## Outcome measures

### Motor skill learning

A dynamic balance task will be used to assess participants' motor learning performance (i.e. motor memory formation). The device consists of a 107 x 65 cm wooden platform (stability platform; Lafayette Instrument Europe; Loughborough, United Kingdom), which is mounted on a fulcrum and has a maximum deviation of 15° to either side. Participants are required to stand with both feet on the platform and try to keep the platform as close to the horizontal as possible during a 30 seconds trial. A millisecond timer measures angular displacement from horizontal during each 30 seconds trial. Participants will be secured with a safety harness and instructed to stand in a comfortable position.

### Primary outcome measure

Description: Change of time in balance (mean angular displacement  $\pm 5^\circ$  from horizontal within each 30 seconds trial) from pre- to post-assessment.

### Secondary outcome measures

#### - Motor skill automatization:

Description: Change of time in balance (angular displacement  $\pm 5^\circ$  from horizontal) in addition to error score of a backwards-counting-task from pre- to post-assessment

- **Transfer effect:**

Description: Change of the achieved score on the FAB - Scale from pre- to post-assessment

- **Muscular endurance:**

Description: Change of time necessary to rise five times from a chair

- **BDNF – Levels:**

Description: Change of peripheral BDNF - concentration from pre- to post-assessment

- **Cardiorespiratory fitness:**

Description: Change in maximum oxygen uptake ( $VO_{2\max}$ ) from pre- to post-assessment

- **General motor function:**

Description: Change in the Parkinson Disease Rating Score (UPDRS) part III (motor part) from pre- to post-assessment

- **Cognitive function:**

Description: Change in the Montreal Cognitive Assessment (MoCA) Score from pre- to post-assessment.

#### Memory consolidation (offline learning):

To assess motor skill consolidation (offline learning) primary and secondary outcomes will be calculated as change scores from the final performance (last practice block) of every practice session to the performance of the first practice block of the following practice session, respectively.

## Study design

In an experimental trial, participants will be randomly allocated to one of two groups (Figure 1). Each experimental arm includes i) a pre-examination 2 - 14 days before ii) six acquisition sessions where the motor skill will be practiced, followed by a retention test iii) 7 days later (Figure 1). On acquisition days, the experimental group will perform a single bout of aerobic exercise (cycle ergometer) immediately following motor practice, whereas the control group will rest in a seated position.

#### Conditions:

**1. Experimental condition:** Participants in the experimental group will practice the ***motor learning task*** followed by a single bout of moderate-intensity ***aerobic exercise*** on a cycle ergometer during acquisition days.

**2. Control condition: Participants in the control group will practice the *motor learning task* followed by a *seated rest* period during acquisition day.**

[figure not shown]

Figure 1 Study Design FaST-PD 3

#### Aerobic exercise bout:

The acute cardiovascular exercise bout comprises a 5-minutes warm-up (intensity will be progressively increased until target intensity), followed by 25 minutes of pedaling at 60–80 rpm and 60% of maximal power output reached in a graded exercise test during pre-examination.

#### Rest:

The resting phase includes seated rest on a chair for 30 minutes. Participants will be permitted to watch selected TV shows during the 30 minutes.

#### Motor skill practice:

Irrespective of group allocation, participants will follow the identical skill practice routine. On acquisition day, participants will perform a familiarization trial followed by 15 practice trials (30 seconds), clustered into 5 blocks of 3 trials, with 60 seconds rest between trials and 120 sec rest between blocks. At a baseline test 7 days prior to and at a retention test 7 days after the intervention period, participants will perform a test consisting of one familiarization trial (to account for potential warm-up effects) and one practice block (3 trials) on the stability platform, respectively.

## Study population

#### **Inclusion criteria:**

Patients are eligible if they have

- a Hoehn and Yahr score of  $\leq 3$ ;
- a score of  $\leq 1$  in the UPDRS item 'postural instability';
- are able to stand and walk independently; and
- are naïve to the motor task.

**Exclusion criteria:**

Criteria for exclusion are

- higher level of cognitive impairment indicated by a score of <21 in the Montreal Cognitive Assessment (MoCA);
- other clinically relevant neurological, internal or orthopedic conditions besides Parkinsonism that would interfere with the exercise paradigm or motor learning task;
- musculoskeletal conditions or surgery 1 year before the study enrolment;
- smoking>10 cigarettes/day or drinking>6 cups of coffee/day or >50 g of alcohol (equivalent of two glasses of wine) consumption/day (Winter et al., 2007).

## Statistical analysis plan

**Power calculation:**

Considering data from previous experiments (Wanner et al., 2020), an a priori estimation of the required sample size for the primary analysis was performed using the statistics program G\*Power (version 3.1.9.4). The estimation was performed for the primary analysis, a 2 (groups) x 6 (training sessions) mixed ANOVA with repeated measures. In order to identify a significant interaction effect of moderate effect size ( $f=0.25$ ), with a statistical power of 80%, and a significance level of  $p\le.05$ , 20 subjects ( $n=10$  per group) need to be included.

**Statistical analysis:**

The effect of aerobic exercise on motor skill learning will be examined by a 2 (groups) x 6 (sessions) mixed ANOVA with repeated measures, testing for the within-subject factor TIME (mean time in balance of all 15 trials in each of the 6 training sessions, respectively) and between-subject factor GROUP (AEX, REST). A separate 2 (AEX, REST) x 6 (last practice block during each training day, first block during subsequent session) ANOVA will be performed to test skill retention between practice sessions.

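### Hypothesis 1 is directional, but the deciding test is a 5-df interaction that can be significant for any large enough non-parallel pattern and gives no estimate of extra learning

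*Combined protocol and SAP*

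**What the plan says.** Under Hypotheses, the first hypothesis has a direction: "Learning a novel balance task over a period of six weeks is enhanced when cardiovascular exercise bouts are performed" directly after each practice session. Under Power calculation, the sample size of 20 (10 per group) is derived for one test: "The estimation was performed for the primary analysis, a 2 (groups) x 6 (training sessions) mixed ANOVA with repeated measures". The target is the interaction: "In order to identify a significant interaction effect" with f = 0.25, 80% power and a 5% level.

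Under Statistical analysis, the same ANOVA is planned: "The effect of aerobic exercise on motor skill learning will be examined by a 2 (groups) x 6 (sessions) mixed ANOVA with repeated measures". TIME is the mean over all 15 trials in each of the six sessions, and GROUP is exercise or rest. The section gives no contrast, direction, follow-up comparison, effect estimate, or rule for which pattern of session means would support Hypothesis 1.

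The Primary outcome measure section defines a single number per patient, the change in time in balance from pre- to post-assessment. The Statistical analysis section contains no test of that change.

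**The concern.** The hypothesis asks whether exercise leads to more learning, and roughly how much more. The interaction asks whether the arm difference is the same in all six sessions. With sessions treated as unordered categories, a significant result says only that the two learning curves are not parallel. Faster learning, slower learning, or a dip followed by recovery can all produce it.

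Two things are at stake. A significant interaction could be reported as support for Hypothesis 1 when the pattern does not show enhanced learning. And even with a real benefit, someone would have to choose the comparison that describes it after seeing the curves, because none is fixed beforehand.

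**Working it through.** **Inputs.** From Power calculation: 2 groups, m = 6 sessions, f = 0.25, alpha = 0.05, N = 20 with n = 10 per arm. Not in the documents, so assumed: correlation between sessions rho = 0.5, equal for all pairs (sphericity, epsilon = 1). These values reproduce the planned N.

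**The plan's own figure.** For the interaction, df1 = (2 − 1)(6 − 1) = 5, df2 = (20 − 2) × 5 = 90, and lambda = f² N m / (1 − rho) = 0.0625 × 20 × 6 / 0.5 = 15. The noncentral F gives power 84.2%. At N = 18, lambda = 13.5 and power is 79.2%. So 20 is the smallest total with equal groups, and the stated size reproduces.

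**What the interaction detects.** Let d be the six arm differences in units of the within-session SD. Then lambda = (n/2) × Σ(d − mean d)² / (1 − rho).

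- Temporary deficit, d = (0, −1, −1, −1, 0, 0). The mean is −0.5, every squared deviation is 0.25, and the sum is 1.5. Lambda = 5 × 1.5 / 0.5 = 15, so power is 84.2%, although the arms are equal in session 1 and at the end.
- Steady benefit or steady harm (linear, scaled to the same lambda): 84.2% each. Simulation of 20,000 trials gave 84.2% (benefit), 84.3% (harm) and 84.2% (temporary deficit).
- Constant difference in all six sessions: every deviation is 0, lambda = 0, rejection about 5% (simulated 5.1%).

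For the temporary deficit, lambda = 7.5 / (1 − rho), so the 84% depends on rho: 50% at rho = 0, 68% at 0.3 and 98% at 0.7.

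**A 1-df alternative on the training sessions.** Take, per patient, the mean of sessions 5 and 6 minus session 1, with weights c = (−1, 0, 0, 0, ½, ½) and Σc² = 1.5. Then lambda = (n/2)(Σcd)² / [(1 − rho) Σc²], tested two-sided on F(1, 18). For a linear divergence scaled to interaction lambda 15, the slope is √(15 / 175) = 0.293 SD per session, Σcd = 4.5 × 0.293 = 1.317, and lambda = 5 × 1.736 / (0.5 × 1.5) = 11.57. Every shape below is scaled to interaction lambda 15, so the interaction has 84.2% power in each row.

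| True arm difference | Contrast lambda | Contrast power |
|---|---|---|
| Saturating (gap to plateau halves each session) | 13.22 | 93% |
| Step after session 1 | 12.00 | 91% |
| Linear | 11.57 | 90% |
| Ramp first seen in session 3 | 9.19 | 82% |
| Accelerating (quadratic) | 8.85 | 80% |
| Ramp first seen in session 4 | 7.81 | 75% |
| Step after session 2 | 7.50 | 74% |
| Step after session 3 | 6.67 | 69% |
| Session 6 only | 3.00 | 38% |
| Deficit in sessions 2–4, then equal | 0 | 5% |
| Benefit in sessions 2–4, then equal | 0 | 5% |

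The contrast overtakes the interaction when its lambda exceeds about 9.82, that is 65% of 15.

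**Serial correlation.** With an assumed lag-1 correlation of 0.7 and a Greenhouse-Geisser correction for the interaction, simulation puts contrast minus interaction power at about +4 points (linear), 0 (step after session 1), +9 (saturating) and −12 (ramp first seen in session 4).

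**The case against.** The strongest reply has four parts.

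*The example is stylised.* A full 1 SD deficit over three sessions with complete recovery is not predicted anywhere. Background raises interference only for exercise before practice, and here exercise follows it. A deficit would also be visible in the session means. This stands: the example shows what the test cannot distinguish, not what is expected.

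*The interaction does not respond to every arm difference.* A reader might infer that any difference makes it significant. It does not: a constant difference leaves it at its 5% level. Since session 1 practice comes before any exercise bout, a difference already present there could not be due to exercise, so this limits the claim rather than adding a defect. The session contrast shares the same blindness.

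*A contrast is not generally more powerful.* A reader might infer that it usually wins, or loses only for a benefit starting after session 3. Neither holds. It also loses for a step after session 2, a ramp first seen in session 3 and an accelerating divergence, and under serial correlation the gain is not dependable.

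*A contrast narrows the hypothesis and does not supply direction by itself.* Hypothesis 1 speaks of learning over six weeks, so faster early learning that later converges is a possible reading, and the session 5–6 contrast would miss it. A two-sided 1-df test also rejects for harm. Both stand, and the second is why the decision rule must include the sign.

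None of this supplies what is missing: a stated rule linking the result to Hypothesis 1, and an estimate of the gain.

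**Conclusion.** The concern holds on interpretability. The plan ties a directional hypothesis to a 5-df test that cannot separate enhancement from other non-parallel patterns, and it plans no estimate of extra learning. The size of the problem is the 84% significance rate for a fully recovering 1 SD deficit, equal to the rate for a steady benefit of the same interaction size. That figure assumes rho = 0.5 and equal correlations; the lack of direction does not depend on them.

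A reader might infer that the sample size is miscalculated or that the change would gain power. The first is not supported by this point: N = 20 reproduces under the stated assumptions. The second depends on the unknown shape of the benefit. The change is worth making because it answers the question asked, and it can be made without new data.

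**What to change.** In the Statistical analysis section:

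1. Prespecify one 1-df between-arm comparison of learning gain, two-sided at 5%, reported in seconds with a 95% CI.
2. State that Hypothesis 1 is supported only if the estimate favours exercise and this test is significant, and that a significant interaction alone is not enough.
3. Preferably use the pre- to post-assessment change, which is already the declared primary outcome and has no planned test. If the decision stays on the training sessions, use the mean of sessions 5 and 6 minus session 1, because session 1 practice precedes any exercise bout.
4. Keep the 2 x 6 interaction as a supporting description of the learning curves.
5. Restate power for the chosen test, giving the assumed correlation.

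The cost is about one paragraph and a new power statement. There are downsides. The session contrast loses power for late or accelerating benefits and misses an early benefit that converges. The pre–post change rests on one 3-trial block at each test rather than 15 trials per session, so it may be noisier. With 10 per arm, a two-sided comparison of change scores has 81% power only for a difference of 1.34 SDs of the change (lambda = 5 × 1.34² = 9.0 on 1 and 18 df). The restated calculation should say whether a difference of that size is realistic.

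### The 2 x 6 ANOVA by default drops any patient with a missing session mean, and the plan states no missing-data rule, analysis population, dropout allowance or sphericity correction

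*Combined protocol and SAP*

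**What the plan says.** The Statistical analysis paragraph of the SAP specifies a 2 x 6 "mixed ANOVA with repeated measures, testing for the within-subject factor TIME". The repeated measure is the "mean time in balance of all 15 trials in each of the 6 training sessions, respectively", so each patient contributes six values. The Power calculation paragraph sizes the trial on the same test: "The estimation was performed for the primary analysis, a 2 (groups) x 6 (training sessions) mixed ANOVA with repeated measures". It arrives at 20 patients, 10 per group, for an interaction of f = 0.25 "with a statistical power of 80%, and a significance level of" 0.05. The Study design section has "six acquisition sessions where the motor skill will be practiced", and the Summary describes "learning a novel motor skill over a six-week period".

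A second ANOVA, also written as 2 x 6, addresses retention between sessions. Its six levels are described as "last practice block during each training day, first block during subsequent session". The section on memory consolidation defines the offline change as running from the last block of a session "to the performance of the first practice block of the following practice session".

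No section says what happens when a session is missed or a patient withdraws. There is no analysis population, no imputation rule, no dropout allowance, no covariance structure and no sphericity correction. G*Power is named for sizing only; no analysis software is named.

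**The concern.** A classical mixed ANOVA needs all six means from each patient. Run in the usual way, it excludes a patient who misses one session and discards the others that patient attended. With 10 patients per arm, each exclusion removes a tenth of an arm, and the comparison is then no longer of all randomised patients. With no rule in place, the choice between dropping, imputing and modelling would be made after the data are seen.

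The offline analysis is exposed in the same way. After a missed session, the plan does not say whether the following session means the next scheduled one (two changes are lost) or the next attended one (one longer interval replaces two). Either way a cell is empty.

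A second gap lies in the same sentence of the SAP. Session means spread over six weeks may correlate less the further apart they are. The interaction test then exceeds its nominal level unless it is corrected, and no correction is stated.

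**Working it through.** **1. Reproduce the planned 20.** Inputs from the Power calculation paragraph: f = 0.25, alpha = 0.05, two groups, m = 6 sessions. The correlation between sessions (rho) and the sphericity parameter (epsilon) are not given; rho = 0.5 and epsilon = 1 are assumed. For the within-between interaction:

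- lambda = f² × N × m × epsilon / (1 − rho)
- df1 = 5 × epsilon; df2 = 5 × (N − 2) × epsilon

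At N = 20, lambda = 0.0625 × 20 × 6 / 0.5 = 15, with df 5 and 90, and power is 0.842. At N = 18, lambda = 13.5, with df 5 and 80, and power is 0.792. The smallest equal-group size reaching 80% is therefore 20, as planned.

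**2. Remove incomplete patients.** The same formula, with N as the number of complete patients:

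| Assumption | N = 20 | N = 18 | N = 16 |
|---|---|---|---|
| rho 0.5, epsilon 1 | 84% | 79% | 73% |
| rho 0.5, epsilon 0.75 | 75% | 70% | 63% |
| rho 0.3, epsilon 1 | 68% | 62% | 56% |
| rho 0.7, epsilon 1 | 98% | 96% | 93% |

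If two patients each miss one session, 120 − 2 = 118 sessions are attended but the ANOVA uses 18 × 6 = 108. Ten attended sessions are discarded.

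**3. What keeping attended sessions recovers.** Simulated with 10 per arm, constant correlation 0.5 and groups diverging linearly:

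- One patient per arm misses only session 3: complete-case ANOVA 78.6%; REML model with random intercept plus AR(1) residuals and Kenward-Roger degrees of freedom 82.1%. That is a gain of 3.5 points.
- Same pattern, with compound symmetry treated as known: 79.2% against 84.1%, a gain of 4.9 points.
- One patient per arm withdraws after session 3: 80.6% against 78.8%, no gain.
- Missed sessions made up: the data are complete, so there is nothing to recover.

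For illustration only, suppose 5% of sessions are missed independently and at random. Then 1 − 0.95^6 = 26% of patients are incomplete, and power is 66.7% (ANOVA) against 79.0% (model). The documents give no rate that would support or exclude this.

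**4. Type I error when correlation decays.** Simulated, complete data, 10 per arm, AR(1) correlation 0.5 / 0.7 / 0.9 (assumed):

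- Uncorrected ANOVA: 6.8 / 7.9 / 8.9%. Separate simulations gave 6.0 to 6.3, 7.0 to 7.4, and 8.9%.
- Greenhouse-Geisser ANOVA: 4.2 / 4.4 / 4.8%.
- Random intercept plus AR(1) model: 4.9 / 4.3 / 2.1%.

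**5. Is one covariance structure clearly best?** Random intercept plus AR(1) data, one patient per arm missing session 3:

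- Groups diverge steadily: Greenhouse-Geisser complete-case ANOVA 61.6%; random intercept plus AR(1) omnibus test 49.7%.
- Difference appears after session 1 and stays: 66.2% against 81.4%.

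The ranking reverses with the shape of the effect. By contrast, an all-data analysis that equals the ANOVA when nothing is missing, with a Greenhouse-Geisser-type correction, gave 66.5% against 61.7% under decaying correlation.

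**6. Count the intervals.** Six practice sessions have 6 − 1 = 5 intervals between them. The Study design and Motor skill practice sections also place a retention test, with one three-trial block, 7 days after the intervention. Counting session 6 to retention gives six.

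**The case against.** The strongest reply is that attendance may be complete or missed sessions may be made up, in which case nothing is lost. The documents neither support nor exclude this. It limits the size of the point but does not supply the missing rule.

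Several stronger readings are tempting, and the documents do not support them.

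- A reader might infer that the plan orders incomplete patients to be dropped, or that it chooses an uncorrected test. It is silent on both.
- A reader might infer that the trial will fall below 80% power. That needs rho near 0.5 and at least two incomplete patients. At rho = 0.7, 16 complete patients still give 93%; at rho = 0.3 the design misses 80% with no losses at all.
- A reader might infer that a model with decaying correlation is what saves the data. It is not: any likelihood-based model on all observed sessions keeps them, compound symmetry included. Decay concerns the type I error, which a Greenhouse-Geisser correction alone repairs.
- A reader might want to make AR(1) mandatory. Its omnibus test can lose 61.6 − 49.7 = 11.9 points under steady divergence, so the figures do not justify that.
- A reader might call 2 x 6 an error for the offline analysis. The retention test could supply the sixth interval, so the text is ambiguous and not plainly wrong.
- A special covariance for the offline changes is also not supported. Simulated type I error for group by interval was 5.3 to 6.3% with a lag-1 Toeplitz structure and 5.6 to 5.9% with compound symmetry.

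Two further cautions stand. A session is both practice and measurement, so a patient who misses session 3 arrives at session 4 with less practice; the simulations ignore this. They also hold the variance constant across sessions.

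**Conclusion.** The point holds as a gap in specification with a modest cost in power. The analysis that sizes the trial excludes incomplete patients by default, and nothing in the plan says otherwise. With rho = 0.5 and epsilon = 1, two incomplete patients take power from 84% to 79%. At 18 complete patients the range is 62% (rho = 0.3) to 96% (rho = 0.7). Using all attended sessions recovers about 3 to 5 points for one missed session per arm, and nothing under early withdrawal or made-up sessions.

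The sphericity gap is separate: about 6 to 9% type I error if correlation decays and no correction is used, and at or below 5% with Greenhouse-Geisser. Both gaps should be closed before data are seen. The pre-to-post change defined under Primary outcome measure does not use the training-session means and is outside this point.

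**What to change.** 1. Analyse every attended session of all randomised patients, as allocated, with a likelihood-based repeated-measures model: REML, Kenward-Roger degrees of freedom, and fixed effects GROUP, SESSION and GROUP x SESSION.
2. Fix the covariance structure, or a sphericity-type correction, before data are seen. Random intercept plus AR(1) is one option but not a requirement, given its possible loss of power under steady divergence.
3. Report the Greenhouse-Geisser-corrected complete-case ANOVA as a sensitivity analysis.
4. Use the same all-observed-data approach for the offline changes, coding any change that touches a missed session as missing. Reconcile 2 x 6 with the number of intervals: five between practice sessions, or six if session 6 to the retention test is included.

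The cost is SAP wording and slightly more analysis work. The model relies on data being missing at random, which absence related to arm or performance could violate, and later sessions may reflect the practice lost at a missed one. It does not replace a dropout allowance; if the sponsor wants one, it should be stated separately (for example, 22 randomised leave 22 × 0.91 = 20.0 after a 9% loss).

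### Session 1 is practised before the first assigned bout, yet it is averaged into an unadjusted GROUP effect; a session-1-adjusted estimate over sessions 2–6 would be a cheap supportive gain, leaving the powered interaction untouched

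*Combined protocol and SAP*

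**What the plan says.** - **Model.** The Statistical analysis section examines motor skill learning with a 2 (groups) × 6 (sessions) mixed ANOVA, "testing for the within-subject factor TIME (mean time in balance of all 15 trials in each of the 6 training sessions, respectively"). Session 1 is one of the six outcome levels. The only other term named in the model is the "between-subject factor GROUP (AEX, REST"). No covariate is named.
- **Order within a day.** Under Study design, "the experimental group will perform a single bout of aerobic exercise (cycle ergometer) immediately following motor practice"; controls rest seated at that point.
- **Practice.** Under Motor skill practice, "Irrespective of group allocation, participants will follow the identical skill practice routine".
- **Test that was sized.** The Power calculation calls this 2 × 6 ANOVA the primary analysis and sizes it on the interaction: "In order to identify a significant interaction effect of moderate effect size" (f = 0.25), with 80% power, significance level .05 and 10 patients per group.
- **Mechanism.** Hypothesis 2 expects that "improved learning outcome with exercise will result from improved motor memory consolidation (offline gains between practice sessions").

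**The concern.** Because the assigned bout comes after practice, exercise cannot have influenced any of the 15 session-1 trials. Session 1 is therefore a baseline measured in the same units as the outcome, and the plan treats it as outcome. Two things follow for the GROUP main effect. Its expected value is diluted, because one of the six averaged sessions carries no effect. And a chance difference in balance ability between two groups of 10 goes straight into it, because nothing adjusts for ability.

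The Statistical analysis section names GROUP as a tested factor, so a GROUP line will appear in the output, and the plan does not say how it will be read. The interaction has 5 numerator degrees of freedom and yields no signed mean difference with a confidence interval. At stake is whether the trial reports a reasonably precise group difference from data it already collects.

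**Working it through.** **Inputs from the documents:** 10 per group, 6 sessions, f = 0.25, significance level .05, session 1 before the first bout. **Assumptions:** unit variance at each session, sphericity, no dropout, and a correlation ρ between sessions, shown as a range.

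**1. The plan's own sample size.** For the interaction, λ = N·m·f²/(1−ρ), with 5 and (N−2)·5 degrees of freedom. At ρ = 0.5 and N = 20, λ = 20 × 6 × 0.0625/0.5 = 15 on 5 and 90 df, and power is 84.2%. N = 18 gives 79.2%. The stated 20 is therefore reproduced at ρ = 0.5, a value the plan does not state.

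**2. What each group comparison estimates.** Let D be the mean effect over sessions 2–6. The effect at session 1 is zero.
- Planned GROUP effect: expectation (0 + 5D)/6 = (5/6)D; variance factor v6 = (1+5ρ)/6.
- Session 1 simply dropped: expectation D; v5 = (1+4ρ)/5.
- Session 1 as covariate: expectation D; va = v5 − ρ² = (1−ρ)(1+5ρ)/5, multiplied by 17/16 for estimating the slope.

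In each case SE = √(2v/10), with v including the 17/16 for the covariate version.

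**3. Relative efficiency.** This is the squared ratio of expected effect to SE, adjusted against planned:

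(36/25)(v6/va)(16/17) = [(36/25)·v6/v5] × [(v5/va)(16/17)]

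The first bracket is the part from dropping session 1, the second the part from the covariate.

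| ρ | v6 | v5 | va | Dropping session 1 | Covariate | Total |
|---|---|---|---|---|---|---|
| 0 | 0.167 | 0.200 | 0.200 | 1.20 | 0.94 | 1.13 |
| 0.1 | 0.250 | 0.280 | 0.270 | 1.29 | 0.98 | 1.25 |
| 0.3 | 0.417 | 0.440 | 0.350 | 1.36 | 1.18 | 1.61 |
| 0.5 | 0.583 | 0.600 | 0.350 | 1.40 | 1.61 | 2.26 |
| 0.7 | 0.750 | 0.760 | 0.270 | 1.42 | 2.65 | 3.76 |

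If correlation instead decays with distance (AR(1)), the total is 1.64 at lag-1 correlation 0.7 and 3.62 at 0.9. The covariate itself pays only above ρ of about 0.13 (AR(1): 0.44).

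The raw SE, which ignores the dilution, falls only above ρ of about 0.22 (AR(1): 0.61). At ρ = 0 it is 0.206 adjusted against 0.183 planned. At ρ = 0.5 it is 0.273 against 0.342.

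**4. Power at ρ = 0.5.** Each pattern is scaled to f = 0.25. For linear growth this implies a 1.46 SD difference at session 6 and D = 0.878 SD. Simulation, 40,000 runs per cell:

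| Effect over sessions | Planned GROUP | Session 1 dropped | Adjusted, 2–6 | Interaction |
|---|---|---|---|---|
| Linear growth | 53% | 67% | 86% | 84% |
| Saturating | 77% | 89% | 98% | 84% |
| Step from session 2 | 87% | 96% | 99.5% | 84% |
| Accelerating | 30% | 39% | 57% | 84% |
| Sessions 4–6 only | 29% | 38% | 55% | 84% |
| Sessions 5–6 only | 16% | 21% | 31% | 84% |

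For linear growth, dropping session 1 supplies 14 of the 33 points gained (67 − 53 out of 86 − 53). At ρ = 0.7 with linear growth, the adjusted test has 93% and the interaction 98%.

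**5. Validity.** Simulated type I error of the adjusted test was 4.9–5.1% over compound symmetry 0 to 0.7 and AR(1) 0.7 and 0.9.

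**The case against.** The strongest reply is that the plan does not rest on the GROUP main effect. The trial is sized on the interaction, learning is naturally a group-by-session question, and a stable imbalance between groups cancels in that test. This stands. The point concerns only the GROUP line and is not a criticism of the powered test or of N = 20.

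A reader might infer from the efficiency table that the adjusted estimate is the better test of the hypothesis and should take over. The documents do not support that. Hypothesis 2 places the benefit in gains between sessions, which may accumulate. For late-building patterns the sessions 2–6 average does much worse than the interaction, and for linear growth at ρ = 0.5 it is only about level.

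Three further inferences go too far:
- *Session 1 precedes all exercise.* The pre-examination includes a graded exercise test (Aerobic exercise bout section). What holds is that session 1 precedes the first assigned bout. The documents also do not exclude that patients know their allocation by session 1, which could affect it slightly.
- *The second ANOVA has the same weakness.* It is described through block performance ("last practice block during each training day, first block during subsequent session"), whereas the Memory consolidation section says "primary and secondary outcomes will be calculated as change scores from the final performance (last practice block) of every practice session" to the first block of the next. Whether levels or changes are analysed cannot be settled from the text, so no claim is made.
- *There is no other baseline.* Motor skill practice includes a pre-intervention test. It has 3 trials against 15 in session 1, and the planned ANOVAs do not use it. It could serve as a covariate, but session 1 offers more trials.

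It is also fair to say that the primary outcome is defined as change from pre- to post-assessment, which this ANOVA does not analyse. That mismatch is a separate matter and has to be resolved on its own.

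**Conclusion.** The point holds as an efficiency improvement confined to the GROUP effect. The planned GROUP test is valid, but it estimates 5/6 of the sessions 2–6 effect whatever the pattern, and it leaves removable between-patient variation in its error. Dropping session 1 from the outcome and adjusting for it was more efficient than the planned GROUP effect at every correlation tried: 1.13 to 3.76 for ρ from 0 to 0.7 under compound symmetry, and 2.26 at the ρ = 0.5 that reproduces the stated sample size. At ρ of about 0.1 or below, the covariate costs slightly and the whole gain comes from removing session 1.

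The 5/6 factor follows from the design alone. The efficiencies also depend on the assumed correlation structure, and the power figures on the assumed effect pattern as well; the documents give neither. The interaction remains the primary test.

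**What to change.** In the Statistical analysis section:

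1. Keep the group × session interaction as the primary test, as sized in the Power calculation.
2. State that the unadjusted six-session GROUP line of the mixed ANOVA will not be interpreted.
3. Add one prespecified supportive estimate: an ANCOVA of mean time in balance over sessions 2–6 on GROUP, adjusted for the session-1 mean, reported as an adjusted difference with a 95% CI.
4. State that this estimate supports the interaction and does not replace it.

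The cost is two or three sentences and one small extra model, with no new data, visits or patients. The downsides to acknowledge are that the estimand becomes the sessions 2–6 average, that the covariate loses a little when sessions are almost uncorrelated (up to about 3 points of power against simply dropping session 1), and that the average is weak for a benefit appearing late (31–57% against 84% for the interaction at ρ = 0.5).
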